**P15-743 (HCV RWE) \_ STATISTICAL ANALYSIS PLAN \_ Final 2.0 \_ 02 Feb 2018**

---

- relapse (HCV RNA <50 IU/mL at EoT or at the last on-treatment HCV RNA measurement followed by HCV RNA  $\geq$ 50 IU/mL post-treatment);
- premature study drug discontinuation with no on-treatment virologic failure;
- missing SVR12 data;
- the percentage of patients achieving SVR24 (single last HCV RNA <50 IU/mL 24 weeks after the last actual dose of the ABBVIE REGIMEN);
- the percentage of patients with virological response (HCV RNA <50 IU/mL) at EoT.

Due to the fact that in the Russian clinical practice tests for HCV RNA often have limit of detection higher than 50 IU/mL (for example, 60 or 100 IU/mL), additional analysis will be performed. In this case all above mentioned effectiveness endpoints will be analyzed with the following definitions:

- the percentage of patients achieving SVR12 (single last HCV RNA value <50 IU/mL or undetectable/negative 12 weeks after the last actual dose of the ABBVIE REGIMEN);
- the percentage of patients with at least one and each of SVR12 non-response categories:
  - breakthrough (at least one documented HCV RNA value <50 IU/mL or undetectable/negative followed by HCV RNA value  $\geq$ 50 IU/mL or positive during treatment);
  - failure to suppress (each measured on-treatment HCV RNA value  $\geq$ 50 IU/mL or positive);
  - relapse (HCV RNA value <50 IU/mL or undetectable/negative at EoT or at the last on-treatment HCV RNA measurement followed by HCV RNA  $\geq$ 50 IU/mL or positive post-treatment);
  - premature study drug discontinuation with no on-treatment virologic failure;
  - missing SVR12 data and/or none of the above criteria;
- the percentage of patients achieving SVR24 (single last HCV RNA value <50 IU/mL or undetectable/negative 24 weeks after the last actual dose of the ABBVIE REGIMEN);
- the percentage of patients with virological response (HCV RNA value <50 IU/mL or undetectable/negative) at EoT.

Achieving SVR12 and presence of breakthrough, relapse or failure to suppress as well as virological response at EoT will be analyzed using univariate logistic regression for both cases (main and sensitivity analyses). These analyses will be of exploratory nature, data driven, and will be repeatedly performed for various CP analysis groups, since not each covariate might be predictive in each patient group. The following parameters can be included in the univariate models as explanatory variables (fixed effect or covariate):

- key demographic information:
  - age;
  - gender;
  - race;
- mode of CHC infection:
  - Most likely mode of HCV infection;
  - HCV Genotype and Subtype;
- HCV RNA level at baseline;
- most recent stage of liver fibrosis:
  - Severity of cirrhosis by Child-Pugh classification;
  - Result of FibroTest;
  - ISHAK Fibrosis Score;
  - METAVIR Fibrosis Score;

- BATTIS/LUDWIG Fibrosis Score;
- KNOPELL Fibrosis Score;
- SCHEUER Fibrosis Score;
- liver and/or CHC related co-morbidities;
- treatment experience (Interferon, Ribavirin, DAA);
- outcome of most recent prior CHC treatment
- laboratory hematology:
  - hemoglobin;
  - platelets;
  - prothrombin time, international normalized ratio (INR);
- laboratory clinical chemistry:
  - ALT;
  - AST;
  - gamma-GT;
  - total bilirubin;
  - albumin;
  - creatinine clearance;
  - alpha-1-fetoprotein.

After univariate model analyses all covariates with a p-value <0.25 in the corresponding univariate logistic regression analysis will be included to multiple logistic regression (MLR) model. MLR will be performing only if more than one explanatory variables will have a p-value <0.25 in the univariate model analyses.

Statistical significant correlated variables with correlation coefficient  $\geq 40$  should be considered and managed. All solutions about choosing explanatory variables will be of exploratory nature, data driven, and will be described with presenting of results of the “*PROC CORR*” SAS procedure.

Backward selection procedures will be applied to generate the final MLR models. A p-value <0.05 will be used for the covariates to stay in the model in a backward elimination step.

The SAS procedure LOGISTIC will be used for the analysis with following statements:

- SELECTION= BACKWARD;
- SLENTRY=0.05.

To avoid the multicollinearity problem all possible explanatory variables will be examined using following SAS script:

```
ods graphics on;  
PROC CORR data=<dataset> plots=all;  
  VAR <variables>;  
RUN;  
ods graphics off;
```

All data for Effectiveness Analyses will be listed in separate listings (for each effectiveness analyses endpoint). Additional listings for NCP population will be created.

---

 Note that all Hematology variables and all Clinical Chemistry should be in the same units. If it is impossible to bring units to the same the smallest units groups will be accepted as missing. If it is impossible to identify the smallest units groups the corresponding covariate will be deleted from the analysis.

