9.4.1.4 HCV RNA Sample

HCV RNA sample – the following needs to be documented:

- **Quantitative HCV RNA by PCR test**
 - Test name and result in IU/mL

Confidential Information

No use or disclose outside AbbVie is permitted without prior written authorization from AbbVie

Version 3.0 (22 Apr 2015) – country v 1.0 dated 26.06.2015

Page 28 of 61

- Lower limit of detection (LLoD) **in IU/mL** and lower limit of quantification (LLoQ) **in IU/mL**
- **Qualitative** HCV RNA by PCR test
 - Test name and result (**positive/n gative**)
 - LLoD **in IU/mL**

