9.7.3 Effectiveness Analysis

The primary effectiveness analysis on clinical outcomes will be performed on all patients in the CP stratified by the CP analysis groups. Due to the non-interventional nature of this study several different methods for determination of the HCV RNA value can be applied. For the purpose of the statistical analysis, a HCV RNA measurement is considered ≤ 50 IU/mL,

- if a PCR test was used
- and the test result is undetectable and the LLoD of the test is ≤ 50 IU/mL or the test result is unquantifiable and the LLoQ is ≤ 50 IU/mL

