9.9 Limitations of the Research Methods

The limitations of observational studies, such as uncontrolled confounding by lack of randomization, and difficulties to clearly interpret treatment effects in the context of missing data are well known. Their validity can be increased by accurate outcome measurements, documentation of the most common confounders, sufficient length of follow-up and by activities to obtain complete recording of available data as well as by searches for missing key data.

The most important outcome measure in this study is HCV RNA. Missing or unrecorded follow-up HCV RNA data can in particular lead to an underestimation of the real SVR rate as compared to the SVR rate of interventional trials. Highly sensitive and quantitative diagnostic tests are required to measure HCV RNA levels in blood. In an observational study each center will be using its own test – either commercially available or so-called “home-brew” tests – which might change from one visit to the next within a patient data set. The challenge is to accurately and consistently document test properties such as the LLoD and the LLoQ to put the results into perspective of prior outcomes from randomized controlled trials with (usually) central laboratory assessments for all trial participants.

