## 9 Effectiveness analysis

Effectiveness analysis will be conducted on *the core population (CP)*, *the target population (TP)* and *the core population with sufficient follow-up data (CPSFU)*.

The results will be reported overall and for scheduled treatment combination ( $\pm$  RBV) and duration (12 or 24 weeks) groups. Additionally and only for *the core population (CP)* the results will be presented for the CP analysis groups by the following parameters:

- HCV genotype and subtype (1a or 1b);
- fibrosis status (the Child Pugh Score class: A, B or C);
- treatment experienced or naïve patients (with/without prior treatment for CHC).

Tables with descriptive statistics will be prepared in accordance with section 7.1. Confidence intervals will be presented according the section 7.2. All corresponding listings will be presented. Additional listings for *the non-core population (NCP)* will be created.

The following effectiveness endpoints will be analyzed:

- the percentage of patients achieving SVR12 (single last HCV RNA <50 IU/mL 12 weeks after the last actual dose of the ABBVIE REGIMEN);
- the percentage of patients with at least one and each of SVR12 non-response categories:
  - breakthrough (at least one documented HCV RNA <50 IU/mL followed by HCV RNA  $\geq$ 50 IU/mL during treatment);
  - failure to suppress (each measured on-treatment HCV RNA value  $\geq$ 50 IU/mL);

---

 Parameter “HCV Genotype and Subtype” from eCRF form “CHC DISEASE CHARACTERISTICS”.

 Parameter “Class” in section “Child Pugh Score” from eCRF form “Liver fibrosis stage”.

 Parameter “Prior treatment for CHC?” from eCRF form “MOST RECENT PRIOR THERAPY FOR CHC”.

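### The additional SVR12 analysis drops the assay-sensitivity limit altogether instead of relaxing it to the 60–100 IU/mL tests it was added for

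*SAP*

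**What the plan says.** **Main analysis.** SAP section 9 defines the endpoint as "the percentage of patients achieving SVR12 (single last HCV RNA <50 IU/mL 12 weeks after the last actual dose of the ABBVIE REGIMEN". The SAP does not restate how an undetectable result is to be read. Protocol 9.7.3 does: it requires a PCR test, and counts the result as meeting the threshold if "the test result is undetectable and the LLoD of the test is" at most 50 IU/mL, or if the result is unquantifiable and the LLoQ is at most 50 IU/mL.

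**Additional analysis.** SAP 2.0 added it on the ground that "tests for HCV RNA often have limit of detection higher than 50 IU/mL (for example, 60 or 100 IU/mL"). The response definition becomes "single last HCV RNA value <50 IU/mL or undetectable/negative 12 weeks after the last actual dose", with matching wording for SVR24 and end-of-treatment response. The failure categories use the counterpart, for example relapse as a value of at least "50 IU/mL or positive post-treatment". No LLoD condition appears in any of these definitions, and *positive* is not defined. The same section also refers to this as the sensitivity analysis.

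**Assay data.** Protocol 9.4.1.4 asks for the LLoD of both quantitative and qualitative tests. Positive/negative is the result format of the qualitative test; the quantitative test reports IU/mL. Protocol 9.9 warns that "In an observational study each center will be using its own test", including in-house tests that may change between visits, and names consistent documentation of LLoD and LLoQ as the difficulty.

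**The concern.** The reason given for the additional analysis covers tests somewhat less sensitive than the Protocol's limit. The rule covers every negative, whatever the sensitivity of the test. A negative from a test that cannot see several hundred IU/mL, or whose limit nobody recorded, gives weaker evidence of cure than a negative at 60 IU/mL, yet both count equally as SVR12.

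At stake is what a difference between the main and additional SVR12 would mean. A reader would take it as the effect of not penalising tests at 60–100 IU/mL. Part of it could instead come from tests far outside that range, including patients with residual viraemia below a poor test's limit. The planned tables do not separate the two sources. The widened definitions also feed the logistic regressions, which SAP section 9 plans for both the main and the sensitivity definitions.

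**Working it through.** **1. The plan's own figure.** The only number tied to this endpoint is the precision statement in Protocol 9.5 and SAP 4.2: 158 patients, 90% response, exact 95% CI 84.2–94.2%. The Clopper-Pearson limits with 158 × 0.90 = 142.2 responders are 84.23–94.20%, width 9.97 points, so it reproduces. With a whole number of responders, 142/158 = 89.9%, CI 84.1–94.1%, width 10.02.

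**2. Both rules applied to the same results.** It is assumed that the main analysis uses the Protocol 9.7.3 condition, which is what makes the SAP's reason for an additional analysis intelligible. The result types below are illustrative, and *positive* is read as a qualitative result.

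| Last result | Main | Additional as written | Additional, LLoD ≤100 |
|---|---|---|---|
| 16, 30 or 49 IU/mL | response | response | response |
| 50, 60 or 500 IU/mL | no | no | no |
| Undetectable, LLoD 12 or 50 | response | response | response |
| Undetectable, LLoD 60 or 100 | no | response | response |
| Undetectable, LLoD 500 or 1000 | no | response | no |
| Qualitative positive, LLoD 12, 50, 60 or 100 | no | no | no |

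Of these 16 results, 5 are responses under the main rule and 9 under the additional rule. Four move to response and none moves the other way. Two of the four (LLoD 60 and 100) are the cases the SAP describes; the other two (500 and 1000) are not.

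**3. Direction.** When both analyses classify the same last measurement, the additional responders include all the main responders. In the core, target and sufficient-follow-up population tables with a fixed denominator, SVR12 therefore rises or stays equal. This does not carry over to the tables that leave out patients with missing SVR12 (Table 2.1.1.1.3 and its counterparts), because the denominator may change. With assumed counts: main 130/135 = 96.3%, with 23 high-LLoD or qualitative-only results treated as missing; if 20 of these are negative and 3 positive, the additional rate is 150/158 = 94.9%, which is lower.

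**4. Size.** One patient is 1/158 = 0.63 points. The documents do not say how many negatives come from tests above 100 IU/mL or of unknown LLoD, so the number *k* is an assumption. If the additional analysis gave 142/158 and *k* of those responders were such negatives, the rate with the limit would be (142 − *k*)/158:

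| *k* (assumed) | SVR12 with limit | Exact 95% CI |
|---|---|---|
| 0 | 142/158 = 89.9% | 84.1–94.1 |
| 8 | 134/158 = 84.8% | 78.3–90.0 |
| 16 | 126/158 = 79.7% | 72.6–85.7 |
| 32 | 110/158 = 69.6% | 61.8–76.7 |

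Eight patients would be 8/158 = 5.1 points, about the planned half-width of 5 points in SAP 4.2.

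**The case against.** The strongest reply is that the primary result is not touched. The main analysis below 50 IU/mL stays in place, the additional table stands beside it, the study is descriptive, and listings are planned for each effectiveness endpoint. A nested definition is also the declared purpose and not a defect in itself. All of this stands, and it limits the weight of the point. It does not explain why a rule meant for tests at 60 or 100 IU/mL has no maximum.

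It is also fair to say that 100 IU/mL is only the SAP's example, so any cut-off is a choice. And Protocol 9.4.1 has data documented only if available, so some LLoDs may be missing. Both argue for a visible row of unknowns, not for leaving the limit open.

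Four stronger readings are tempting, and the documents do not support them:

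- **The additional analysis can only raise SVR12 everywhere.** This holds for fixed denominators only (step 3).
- **A low quantified value is counted as both responder and failure.** This needs *positive* to mean any detected RNA. Protocol 9.4.1.4 ties the word to the qualitative test, so a lone 30 IU/mL is a responder only. What remains open is a visit with both a low number and a qualitative positive. A bare positive from a sensitive test counted as failure is conservative, not contradictory.
- **The analysis was tailored to the data.** It was added on 2 February 2018, after the planned end of data collection in August 2017. But SAP section 2 allows revision before soft lock, the revision history gives the reason, and no lock date is stated.
- **SVR12 is inflated by a known amount.** No passage reports any test with an LLoD above 100 IU/mL.

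**Conclusion.** The point holds, for the additional analysis only. Its response rule is wider than the reason given for it: it removes the Protocol's sensitivity condition where the reason supports only relaxing it. Followed as written, it counts negatives from tests of very low or unknown sensitivity as SVR12, SVR24 and end-of-treatment response. In the fixed-denominator tables the effect on SVR12 is upward or nil. Its size is unknown: 0.63 points per affected patient at N = 158, and zero if no such tests were used.

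The undefined *positive* is a gap in wording, not a demonstrated double count.

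The conclusion assumes that the main analysis applies Protocol 9.7.3 and that both analyses use the same last measurement. The SAP cites Protocol 4.0 of 11 July 2017; the Protocol available here is version 3.0 (country version 1.0), so a later assay rule cannot be excluded. The change is worth making, but the primary result does not depend on it.

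**What to change.** In the additional analysis of SAP section 9:

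1. Count an undetectable or negative result as response only with a documented LLoD up to a stated maximum. The value 100 IU/mL is a natural candidate, being the highest the SAP cites; if another is chosen, give the reason.
2. Show negatives above that maximum, or with unknown LLoD, in a separate row.
3. Tabulate SVR12 by LLoD band: ≤50, 51–100, and >100 or unknown.
4. State that *positive* applies only to qualitative results without a numeric value, and that a numeric value takes precedence where both exist.
5. Check the wording against Protocol 4.0, and list the relaxed assay rule in SAP section 16 if it departs from that version.

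The cost is a few lines of SAP text and one small table, using the LLoD field that Protocol 9.4.1.4 already asks for. The additional SVR12 may come out slightly lower. The rescue of tests at 60–100 IU/mL is kept, and the main analysis does not change.

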9.7.3.3 Statistical Methods for Analysis of Effectiveness Variables

The simple percentage of patients achieving SVR12 will be calculated and an exact two-sided 95% confidence interval (CI) of the percentage will be computed based on the Clopper-Pearson method.

Corresponding methods will be used for other response rates (EoT response rate, relapse rate, viral breakthrough). The relapse rates will be estimated in patients of the CP analysis groups with EoT response and sufficient HCV RNA measurements post-

treatment. Viral breakthrough rates will be estimated in all patients of the CP analysis groups, who have at least one undetectable HCV RNA measurement on-treatment and at least one on-treatment or EoT measurement thereafter.

Univariate and multiple logistic regression (MLR) methods will be used to investigate the impact of the following explanatory covariates on SVR12:

- Key demographic information
- Mode of CHC infection
- HCV RNA level at baseline
- Most recent stage of liver fibrosis
- HCV genotype and subtype (if available)
- Type of treating institute
- Liver and/or CHC related co-morbidities
- Key clinical chemistry and hematology laboratory variables at baseline
- In treatment experienced patients only:
 - Most recent prior treatment for CHC
 - Outcome of most recent prior CHC treatment

Further details and additional covariates will be specified in the SAP.

These analyses will be of exploratory nature, data driven, and will be repeatedly performed for various CP Analysis Groups, since not each covariate might be predictive in each patient group. Furthermore, the fact that treatment regimens will differ in the various patient groups has to be taken into account, when selecting the patient groups for each MLR analysis. Backward selection procedures will be applied to generate the final MLR models which consider only covariates in the selection procedure with a p-value <0.25 in the corresponding univariate logistic regression analysis. A p-value <0.05 will be used for the covariates to stay in the model in a backward elimination step. Logistic regression methods will also be used to investigate the impact of treatment adherence on SVR12.

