### **7.3 Missing Data**

No data will be imputed for any effectiveness or safety analyses.

If information about adverse event start date and time is missing or incomplete, the following rules (table 7.1) will be used for the classification of AEs for AEs of the study period and AEs, which occurred before the start of treatment.

Table 7.1 – AEs missing management.

| Day        | Month      | Year       | Processing   |
|------------|------------|------------|--|
| is missing | is known   | is known   | AE will be classified as AE of the study period, if month and year $\geq$ month and year of the first study drug administration date |
| is missing | is missing | is known   | AE will be classified as AE of the study period, if year $\geq$ year of the first study drug administration date                     |
| is known   | is missing | is known   |  |
| is missing | is known   | is missing | AE will be classified as AE of the study period  |
| is known   | is missing | is missing |  |
| is missing | is missing | is missing |  |

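### SAP 9 offers the outcome of the last prior treatment to all predictor models with no level for naive patients, so if it passes screening the overall and mixed-subgroup regressions can lose every naive patient

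*SAP*

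**What the plan says.** **Protocol.** Section 9.7.3.3 lists the covariates for the SVR12 regressions. Two of them, the most recent prior treatment and "Outcome of most recent prior CHC treatment", stand under the sub-heading "In treatment experienced patients only". Section 9.4.1.1 asks for prior therapy and its outcome only where the patient is treatment-experienced. Section 9.2.1 admits both naive and experienced patients.

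**SAP.** Section 9 introduces one list for all groups: "The following parameters can be included in the univariate models as explanatory variables (fixed effect or covariate". In that list "outcome of most recent prior CHC treatment" appears with no restriction. Then "all covariates with a p-value <0.25 in the corresponding univariate logistic regression analysis will be included to multiple logistic regression (MLR) model". The final model comes from PROC LOGISTIC with "SELECTION= BACKWARD". On missing values, section 7.3 says: "No data will be imputed for any effectiveness or safety analyses".

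The shells in section 18 put the overall core-population models first (Tables 2.2.1.1.1 and 2.2.1.2). They are then repeated with and without ribavirin, by Child Pugh class, and with and without treatment experience, and again for the target population and the core population with sufficient follow-up. SAP section 16 declares the methods consistent with the protocol and names only the dropped patient-support-programme regression as a change.

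**The concern.** A naive patient has no prior treatment and so no outcome of it. The value is absent by design, not by accident of follow-up. A logistic model that needs complete records can hold this variable and the naive patients together only if naive is coded as a level, and the SAP defines no such level for it.

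The regressions serve secondary objective 2 (Protocol 8.2.2), predictive factors of response. If the variable enters, a model labelled overall describes experienced patients only. The other covariates will have been screened with naive patients included and then fitted without them. The multiple regression can no longer estimate any naive-versus-experienced contrast. The same applies to the ribavirin and Child Pugh subgroup models, which also mix the two kinds of patient.

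Entry is plausible. Protocol 7.1 reports 80% SVR in cirrhotic genotype 1a prior null responders treated for 12 weeks, with higher rates in partial responders and relapsers.

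**Working it through.** **1. The plan's own figure.** Clopper-Pearson limits are the beta quantiles B(0.025; x, n−x+1) and B(0.975; x+1, n−x). With n = 158 and x = 0.90 × 158 = 142.2 they give 84.23% to 94.20%, width 9.97%. This agrees with the 84.2% to 94.2% in Protocol 9.5 and SAP 4.2. So 158 patients and 90% SVR12 are used as the starting point, with 158 × 0.10 = 15.8 expected failures.

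**2. The mechanism, from the documents.**
- Naive patients are eligible (Protocol 9.2.1).
- The outcome is documented only for experienced patients (Protocol 9.4.1.1).
- Nothing is imputed (SAP 7.3), and no naive level is defined for this covariate (SAP 9).
- Every screened variable with p<0.25 goes into the starting model, followed by backward elimination (SAP 9).

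Two assumptions complete it: the field is blank for naive patients, and PROC LOGISTIC keeps its default of using only records complete on every variable in the starting model. Under that default the naive patients stay out of the whole backward run, even if this variable is eliminated at a later step.

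**3. Check on illustrative data.** In 158 artificial records, 79 of them naive, a model with age alone used 158. Adding prior-treatment outcome left 79. Recoding the blanks as a naive level restored 158.

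**4. Size.** The documents do not give the naive share f, so a range is assumed. Patients left = 158 × (1 − f); failures = patients left × (1 − SVR12).

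| Naive share (assumed) | Patients left, at most | Failures at 90% SVR12 | Failures at 95% SVR12 |
|---|---|---|---|
| none lost | 158 | 15.8 | 7.9 |
| 30% | 158 × 0.7 = 111 | 11.1 | 5.6 |
| 50% | 158 × 0.5 = 79 | 7.9 | 4.0 |
| 70% | 158 × 0.3 = 47 | 4.7 | 2.4 |

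These are upper bounds, because other incomplete covariates in the same starting model remove further records.

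**5. How often a variable with no effect would enter.** Its univariate model already uses experienced patients only, so n is 111, 79 or 47. This was simulated with 10% failures and a Wald test at 0.25. A balanced binary outcome at n = 111 enters about 24% of the time. A three-level outcome (assumed split 40/40/20) enters about 16%, 10% and 4% of the time at n = 111, 79 and 47, to within about one percentage point. Sparse failures make the Wald test conservative, so the nominal 25% is a ceiling that is reached only in the favourable case. A variable with a real effect would enter more often.

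**The case against.** **The loss would be visible.** One might infer that naive patients vanish silently. They do not: the shells for both the univariate and the multiple regressions print the number of patients analysed. This stands. What the tables would not show is that the missing patients are the whole naive stratum.

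**The SAP may not have removed anything.** A reader might conclude that the SAP dropped a protocol restriction. SAP section 2 says it was written from Protocol version 4.0 of 11 July 2017; the protocol supplied is version 3.0, country version 1.0. The difference is established only against the supplied version. The gap in the SAP's own rules does not depend on that comparison.

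**The analyst has discretion.** Covariates can be offered to the univariate models, and choices are described as exploratory and data driven. This stands in part. Once a variable is screened, entry below 0.25 is mandatory, and the only discretion then described concerns correlated variables.

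**Naive may have its own code.** The CRF is not supplied, so a blank is inferred from Protocol 9.4.1.1. The SAP's shells use a naive group for prior-treatment subgroups. If the same coding is meant for this covariate, SAP 9 needs to say so.

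**Other covariates lose records too.** The same list holds five biopsy scores, while the liver-stage shell also allows non-invasive and clinical staging. This is correct, and it is why 158 is only an upper bound. It is a separate gap.

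**Other analyses survive.** SVR12 is reported by prior-treatment status, the regressions are repeated in each of those groups, and treatment experience has its own univariate model. This stands.

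**Conclusion.** The point holds as a conditional defect in an exploratory secondary analysis, and it should be corrected. Followed as written, SAP 9 can turn the overall and mixed-subgroup multiple regressions into models of experienced patients only. That requires three things: the variable is offered and passes p<0.25, naive patients are blank on it, and the procedure runs on complete cases. At an assumed naive share of 30%, 50% or 70%, at most about 111, 79 or 47 of 158 patients and about 11, 8 or 5 failures remain at 90% SVR12.

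The documents do not support saying that this is certain to happen, or that a no-effect variable would trigger it one time in four whatever its coding. With three levels the chance is about 16%, 10% or 4%, and it is smallest where the loss of patients is largest. The primary SVR12 estimate and its confidence interval are untouched, as are the separate naive and experienced subgroup analyses.

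**What to change.** In SAP section 9:

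1. Offer the outcome of the most recent prior treatment only in the models confined to treatment-experienced patients.
2. In the overall and mixed-subgroup models, use a single prior-treatment factor with naive as its own level (for example naive, relapse, non-response, other or unknown, following the CRF codes). Let it replace both the outcome variable and the overlapping treatment-experience variable, so that the same information is not entered twice and this covariate removes no naive patient.
3. Reconcile the text with Protocol version 4.0 and, if it differs, record the change in SAP section 16.

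The cost is a few lines of SAP text and a recode of data already collected. The number analysed is already in the shells. Record losses from biopsy scores and other incomplete covariates are a separate matter that this change does not address.
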